Participants in the ACO stakeholder key informant interviews, caregiver interviews, and caregiver or youth focus groups will be provided a fact sheet with details about the study at the start of the interview. All participants will be told that they may decline to participate, decline to be recorded, refuse to answer any question, or discontinue participation at any time. While many of the ACO key informants will be employees of the ACO, we will emphasize that their participation is completely voluntary and will in no way affect their employment with the ACO or Nationwide Children's Hospital. Focus group participants and caregiver interviewees may be patients (or parents of patients) of providers associated with the organization being studied; thus, we will emphasize that their participation is completely voluntary and in no way will affect their ability to obtain care, their relationship with Partners For Kids, Nationwide Children's Hospital or their interaction with their doctor(s). The PI or study investigator will review the fact sheet with participants, ask for and address any questions they may have, and then request verbal informed consent/assent in all cases EXCEPT for the youth focus groups, in which case written consent will be requested. If the participant provides consent/assent, then the study investigator will proceed with the interview or focus group using the interview or focus group guide. Additionally, in the case of teenagers participating in the youth focus groups, we will obtain written informed assent from the teenager participant.

All interviews and focus groups will follow the list of questions and topics in the respective guides prepared by research staff with consultation from the patient advisory panel. The interviews and focus groups are semi-structured in the sense that additional, follow-up questions will be asked to probe comments made by participants. Interviews with ACO stakeholders and with caregivers will last about 1 hour. Focus groups will last about one and one half hours. All interviews and focus groups will be digitally recorded and subsequently transcribed.

STEPS – Youth Focus Groups (see IRB)

1. Post flyers, send recruitment email (list document names)
2. Youth call [contact] number or send email to [contact] – can leave a confidential message (write out confidential message)
3. Ascertain eligibility (form name:)obtain verbal assent during telephone recruitment
4. In lieu of signed parental permission, we will provide study information to parents over the phone and gain parental consent for participation and receiving a gift card. . Specifically, when the youth call about the study, we will ask to speak to a parent and describe the study to the parent. If the parent approves of the youth's participation, we

will continue with enrolling the youth into the study. If the parent does not wish for the youth to participate, we will thank the parent for his/her time and conclude the call.

5. If a parent is not available over the phone, we will ask the youth for an address and mail a fact sheet to the parent prior to the focus group. The fact sheet has clear information about whom to call should the parent not want their child to participate. The youth will need to have the parent call back or come with the youth to the focus group to obtain verbal or signed parental permission
6. Mail or email directions to the youth.
7. ARRIVING AT FOCUS GROUP. Signage will be placed to guide participants to the proper location. At the focus group we will provide the participants with an additional copy of the fact sheet and then written assent when the focus group convenes.

STEPS – Parent/Caregiver Focus Groups (see IRB)

1. Caregivers call [contact] number or send email to [contact]– can leave a confidential message (write out confidential message)
2. Ascertain eligibility (form name:) obtain verbal consent during telephone recruitment
3. Mail or email directions to the caregiver.
4. ARRIVING AT FOCUS GROUP. Signage will be placed to guide participants to the proper location. At the focus group we will provide the participants with an additional copy of the fact sheet and then written assent when the focus group convenes.

STEPS – Parent/Caregiver Interviews (see IRB)

1. Post flyers, send recruitment email
2. Caregivers call [contact] number or send email to [contact]– can leave a confidential message (write out confidential message)
3. Ascertain eligibility (form name:)obtain verbal assent during telephone recruitment
4. Mail or email directions to the participant.
5. ARRIVING AT INTERVIEW. Signage will be placed to guide participants to the proper location. At the interview provide participants with an additional copy of the fact sheet.

We will use the same methods for analyzing all of the data gathered for Aim 1. Following standard qualitative coding techniques, we will code data segments within transcripts using labels that capture ideas contained in the data. Related codes will then be grouped into themes that highlight common perceptions, ideas, or experiences across informants. We will follow an iterative approach to analysis that involves ongoing cycles of reading and coding transcripts, reviewing the literature, and discussing findings among the research team to identify themes. Throughout the process we will use the constant comparative method comparing data with data, data with codes, codes with codes, and codes with themes, in order to construct a detailed framework of perceptions regarding the effectiveness of care coordination strategies.

The research team will use the Atlas.ti software package (version 9.0) to facilitate the managing and coding of qualitative data. Our study investigators have used this approach in several previous studies. Using all of the qualitative data (i.e., focus groups and ACO stakeholder and caregiver interviews), we will identify the advantages and disadvantages of each model and the situations under which each model is likely to be more or less effective based on patient and stakeholder perceptions of outcomes. We acknowledge that the retrospective nature of Aim 1 may affect recall. However, our intent will be to understand the perceptions of various stakeholder groups regarding care coordination under the two models, as well as, their experiences before, during and after the policy change. Under this aim we will investigate the extent to which participants perceive care coordination to have changed and their own assessments of the effects of any such changes.

Interview data collected from ACO stakeholder participants will be identified only by position title, not by name. Similarly, for interviews and focus groups with caregivers and youths, participants will be identified only by number, not by name. Participants' comments will not be quoted in such a way as to disclose their identity. All data will be reported either in aggregate, summary, or individually de-identified form.

Aim 2

Caregiver Survey Methodology

The FECC will be administered by the Carolina Survey Research Lab (CSRL) at the University of North Carolina at Chapel Hill. Survey steps are outlined below:

- The ACO (PFK) mails letters to potentially eligible enrollees describing the study and offering them the option of opting out of the sampling frame. Contact information for those who do not opt out will be sent to CSRL for survey contact.
- CSRL will send letters to all non-opt out families. The letter will include thanks for willingness to participate, telephone survey logistics, and a web address that can be used to complete the survey on their own. We expect up to five percent of respondents to use the web-based survey.
- Trained interviewers will make up to 10 telephone attempts for each caregiver who does not complete the online survey. When telephone numbers are found to be non-functional, research staff will make reasonable efforts to find working numbers through use of Lexus-Nexus and through working with PFK staff with access to electronic medical record (EMR) information that may offer updated contact information.
- Surveys will be conducted using a computer-assisted telephone interviewing (CATI) system with interviewer performance monitored through review of randomly selected taped interviews.
- Prior to the close of the interview, the interviewer will request verbal consent for a review of care coordination documentation in their medical records and for linking of their survey responses to medical record and claims data.
- All individuals who complete the interview will be mailed a \$20 gift card in appreciation of their participation.

Key Decisions

- We will keep the survey wording the same because it has been field tested and underwent cognitive development testing.
 - It is not necessary to allow for N/A (for e.g. 5E – needing equipment, in all the piloted work this was never an issue).
 - Refusals or don't know – they may not be read, but interviewer can fill it in. If subject says they don't know, record in notes and leave unanswered or say respondent refused. For programming purposes, refuse/don't know is a (non-read) option. Email-based surveys can allow blanks (in fact are mandated to allow).
- Web survey
 - We will pilot the web survey.
 - CSRL will do in-house.
 - We will also pilot with Patient Advisory Panel prior to April 6th patient advisory panel meeting.
 - We will work on web survey first to make sure it is available for pilot testing, and then focus on the phone survey.
 - CSRL will mail the follow-up letter to non-opt-out families with a web link and code. Participants will have one month to answer. After the month, CSRL will discontinue access to the web and then will know which part of the sample remaining to be called.
- Eligibility/Survey Administration
 - NCH will provide a summary of demographic data on opt-outs.
 - Families with more than 2 eligible patients – ask about the patient (i.e. child) for whom the interviewer is calling only.
 - Interviewer will ascertain which caregiver is the one who obtains health care/ the most involved in going to health care visits with the child and interview this person.
 - At end of survey, interviewer will confirm to whom the check should be mailed and confirm mailing address – participant can choose any person to send check to.
 - We will add 'Yes I agree, No I don't agree' for consent box at the end of survey – this will serve as documentation that interviewer obtained verbal consent.
- Reporting
 - CSRL will provide weekly reports on calls that will include such information as: bad numbers, number called, number ineligible, those we haven't screened, screened but declined, and completed, and medical record consents. May also include how long the interview has taken and profiling.

Timeframe

March 1 UNC provide CSRL with all IRB-approved materials, including consent

materials, screener, and the survey in both English and Spanish.

March 27	CSRL send web-based survey link for pilot testing with the patient advisory panel.
March 27- April 5	Patient advisory panel members pilot the web-based survey.
April 6	Quarterly Advisory Panel Meeting – investigators solicit PAP input including such things as need for more instructions, navigation issues, using the interface (do links work, etc.), is survey user-friendly.
April 10	UNC provide feedback about the web-based survey to CSRL
May 1	PFK mail out opt-out letters.
May 31	Preliminary demographics due to PCORI (prepared by NCH).
June 9	End of 40-day period.
June 23	NCH send eligible sample to CSRL.
July 1	Begin web survey. CSRL send follow-up letters to eligible sample with code and web address.
July 31	End date for web survey.
August 1	Begin telephone survey.
October 31	End date for telephone survey.
Nov 30	CSRL send final dataset to UNC.

Medical Record Review

Based on our pilot work, we expect that 1,000 caregivers who complete the phone survey will also provide consent for abstraction of their medical records for MR based care coordination measures. Data for Medical record-based care coordination measures will be collected primarily through review of the Epic EMR at Nationwide Children’s Hospital (NCH) conducted by an experienced, trained NCH abstractor using a field-tested data abstraction tool. The integrated EMR at NCH allows review of NCH inpatient visits and primary and specialty care services provided by physicians in the NCH system. We estimate 50% of ABD children enrolled in PFK were seen in the NCH system in the past year. If a participant lists a main provider outside of the NCH system, a copy of the relevant medical records will be requested from that provider for review. The first 20 records will be re-reviewed by a second abstractor for quality control and training.

Aim 3

Assumptions

- PFK data and claims data are housed on servers at NCH.

- NCH has permission from PFK to use data.
- NCH has permission from the state to use data.
- NCH will provide a limited de-identified dataset at the person-month level.
- Data will be provided in SAS and STATA format.
- Data will be available for download from a secure server using a double-password system.
- [name], [name], [name], [name], and the NCH programmer will have access to the data.

Steps for Data Preparation and Access

1. [name] and [name] will develop a programming guide for the programmer.
2. NCH Programmer links PFK and state data (EHR data, claims data) to study data (caregiver data) and strips identifiers.
3. NCH Programmer creates an analytic file.
4. NCH Programmer runs frequencies.
5. NCH Programmer makes de-identified dataset available in both SAS and Stata formats.
6. NCH will notify team that data are available for download.
7. [name] will log on to server using double-password system (VPN-like system).
8. [name] will download and house data on secure site at UNC & OSU.

Dissemination Plan

The Patient Advisory Panel will assist us in developing our final dissemination plan. The patient-centered quality of the research will ensure that the findings disseminated to policy-makers and providers also emphasize patients and caregivers, alerting them to the importance of these groups in their decision-making going forward. The results of our research might be disseminated through various stakeholder groups, including families of disabled children, child disability advocacy groups, state Medicaid agencies, policy makers and ACO and health system leaders. In addition to the dissemination activities included in our proposal, the results of this research could be disseminated through stakeholder newsletters, webinars, websites, patient or community conferences, news media outlets and issue briefs. Target stakeholder meetings and conferences will include the AcademyHealth Annual Research Meeting and National Health Policy Conference and the Pediatric Academic Societies/Ambulatory Pediatrics Association Complex Care Special Interest group meeting, Target journal for publication will include *Health Affairs* and *Pediatrics*.

The results of this research have real potential to be implemented in other settings, namely in other ACOs. In the wake of the Affordable Care Act, ACOs are developing across the country. Medicare ACOs have largely dominated the ACO market, however, there is increasing interest and growth in Medicaid and pediatric ACOs. Our research involves one of the most highly regarded pediatric ACOs in the country and pediatric ACOs across the state of Ohio and elsewhere are likely to look to results from our research to help guide their care coordination efforts for ABD children.

Collaborating Organizations, Personnel, Project Roles

University of North Carolina at Chapel Hill

[name], Associate Professor, will serve as Principal Investigator. As such she will lead the project's efforts and assumes overall responsibility for completing project milestones according to the PCORI contract.

[name]., Professor, will serve as Co-Investigator with primary responsibility for Aim 3. She will work together with [name] of OSU to conduct quantitative comparative analyses using survey, medical record, and claims data. She will also contribute to the quantitative analyses under Aim 2 and the cross-aim analyses under Aim 3.

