There are approximately 1.3 million children in the United States who have physical or behavioral health conditions resulting in significant functional impairment [1]. In Ohio, there are approximately 38,000 ABD children.[34] They represent 3.4% of all Ohio Medicaid children, yet they account for 16.2% of all spending for Ohio Medicaid children ages 0-18.[34] The average monthly cost per ABD Medicaid child is \$1,188 compared to \$205 per month for all other Medicaid children.[34] The involved care needs of these ABD children, along with concerns about health plans’ provider network adequacy, experience, and willingness to serve this population, have been long considered great enough to exempt them from the managed care enrollment required of other Medicaid-eligible children and to leave them instead in the traditional fee-for-service system.[2] However, faced with increased pressure to improve care for beneficiaries with complex needs and address budgetary concerns, several states now mandate managed care enrollment and/or are investing in alternative models such as ACOs for the pediatric ABD population.[31] The significance of this study is that it compares the effectiveness of care coordination for disabled children under two models of health care delivery—fee-for-service and ACO.

Projected Use of Study Results

- By health systems (including PFK specifically and others more generally) who want to understand the advantages and disadvantages of an ACO model for coordinating the care of children with disabilities and to plan more effective approaches to care for this population.

- By patients and families considering participating in an ACO—results offer them information for understanding the advantages and disadvantages as compared to a more traditional fee-for-service health plan.

Study Design

General Approach

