The proposed study uses a recent policy change in Ohio as a natural experiment to assess outcomes and experiences of ABD children and their caregivers in an ACO model of care compared to their previous outcomes and experiences in a traditional fee-for-service model. Prior to the policy change, nearly all of the 38,000 Medicaid-eligible ABD children in Ohio were enrolled in a traditional fee-for-service plan. After the policy change went into effect in July 2013, all ABD children were required to enroll in managed care. In central and southeastern Ohio, the policy change effectively moved approximately 8,000 Medicaid-eligible ABD children into the *Partners for Kids* (PFK) ACO.

PFK is the nation's largest and oldest pediatric ACO focused solely on Medicaid-enrolled children. Established in 1994, PFK is a not-for-profit physician hospital organization jointly owned by Nationwide Children's Hospital in Columbus, Ohio and by a 750+ physician group comprised of primary care physicians, pediatricians, and specialists. In 2013, Nationwide Children's Hospital served 1,000,000 patient visits, 21,000 annual inpatient admissions and 68 facilities including outpatient centers, urgent care, research, and primary care and specialty physician offices. As an ACO, PFK currently provides both primary and specialty care to more than 300,000 Medicaid children enrolled in one of 5 Medicaid managed care plans operating in 34 counties (out of 88 total counties in Ohio) stretching from urban Columbus to rural Appalachia.

Research Questions

The proposed study will address the following research questions:

- 1) Can an ACO implement a system of care coordination that improves upon what children with disabilities and families received before becoming part of an ACO?; and
- 2) What effects do these activities have on health care and outcomes?

Hypothesis

Children with disabilities will have improved outcomes and experiences after becoming part of an ACO compared to their prior outcomes and experiences in a traditional fee-for-service model.

Study Aims

Aim 1

Use qualitative methods to identify stakeholder perspectives on care coordination before and after the transition from fee-for-service to the ACO model of care for children with disabilities.

Aim 2

Implement a novel caregiver and medical record abstraction tool designed to assess care coordination for children with special health care needs to evaluate the quality of care coordination provided by the ACO.

Aim 3

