We will use the same methods for analyzing all of the data gathered for Aim 1. Following standard qualitative coding techniques, we will code data segments within transcripts using labels that capture ideas contained in the data.[37,38] Related codes will then be grouped into themes that highlight common perceptions, ideas, or experiences across informants. We will follow an iterative approach to analysis that involves ongoing cycles of reading and coding transcripts, reviewing the literature, and discussing findings among the research team to identify themes. Throughout the process we will use the constant comparative method comparing data with data, data with codes, codes with codes, and codes with themes, in order to construct a detailed framework of perceptions regarding the effectiveness of care coordination strategies. [39,40] The research team will use the Atlas.ti software package (version 9.0) to facilitate the managing and coding of qualitative data. Our study investigators have used this approach in several previous studies.[41–44] Using all of the qualitative data (i.e., focus groups and ACO stakeholder and caregiver interviews), we will identify the advantages and disadvantages of each model and the situations under which each model is likely to be more or less effective based on patient and stakeholder perceptions of outcomes. We acknowledge that the retrospective nature of Aim 1 may affect recall. However, our intent will be to understand the perceptions of various stakeholder groups regarding care coordination under the two models, as well as, their experiences before, during and after the policy change. Under this aim we will investigate the extent to which participants perceive care coordination to have changed and their own assessments of the effects of any such changes.

Aim 2

In Aim 2, we will add to our qualitative assessment of care coordination and perceived changes in care coordination, using a newly developed quantitative care coordination measurement tool. This tool will measure experiences with and documentation of care coordination in the first year after the transition to the ACO. Data from this measurement will be used to describe the extent of care coordination, to assess whether measured care coordination is consistent with expectations identified in Aim 1, and to measure the relationships between care coordination and patient-centered utilization outcomes.

Caregiver Survey

Participants & Sample Size

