Administrative data-derived measures include items such as continuity of care, use of the emergency department, hospitalizations, and access to primary and specialty care, timely follow-up after initial prescriptions of ADHD medications or after psychiatric hospitalization.[45,46] We will incorporate recent methodological advances in operationalizing these measures from administrative data.[47] All study measures will be reviewed with our Patient Advisory Panel in order to prioritize the measures determined to be of greatest importance to our patient population. The Patient Advisory Panel may also propose and prioritize additional patient-centered outcome measures during the first two years of the project.

Key treatment variable: The key variable of interest is the enrollment in the ACO by children with disabilities. This “treatment” was assigned to children seen by one of the health care facilities within PFK’s 34-county service area in Ohio beginning in July 2013. Data from PFK-enrolled children prior to enrollment (July 2010 – June 2013) will serve as primary controls, adjusting for age and length of time on Medicaid. Children who were enrolled in Ohio Medicaid with ABD eligibility in other areas of the state will serve as additional potential controls using Medicaid claims data. We cannot use these children as primary controls due to important limitations in the data, namely the inability to attribute children to other ACOs outside the 34 county PFK region. PFK’s unique arrangement with the state allows us to clearly identify the ACO catchment area by county and thus we can clearly attribute these patients to PFK.

Patient Characteristics: Our analysis is conducted on a diverse population of children and adolescents. Their characteristics vary by age, gender, race, Latino ethnicity, SSI status, county of residence, diagnoses, procedures received, length of time on Medicaid and other patient characteristics as detailed in **Appendix F**. We will create baseline disease adjustment categories using the Chronic Illness and Disability Payment System, which was specifically designed for disabled Medicaid enrollees. [48]

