Methods: Following the latest guidance on PCOR methods from the PCORI Methodology Report, we will define the analysis sample that represents the distribution of demographic and conditions among ABD children in Ohio from histories available in the administrative data.[49] We will use approaches appropriate to PCOR including mixed qualitative and quantitative methodologies in a quasi-experimental study design for this Aim.

Quantitative Analysis: Using the interrupted time series analysis for statistical models, we will estimate the effect of switching from FFS to ACO while controlling for secular trends. This method examines both the change in the average level of each outcome in the post period as

compared to the pre-ACO period, as well as changes in the trends in each outcome. For example, an interrupted time series analysis can determine whether access to outpatient visits with specialists increases or decreases after the children are enrolled in PFK as well as whether changes in the rate of access over time are greater or lower as compared with the pre-ACO period. Outcome models will be run separately on each outcome using generalized estimating equations with appropriate distributional assumptions for each type of outcome variable (e.g., binary, continuous). The key variables will be an indicator of the ACO enrollment period and its interaction with time trends.

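### The Aim 3 time series has no transition period around July 2013, so a temporary disruption, if there was one, would appear as an initial worsening followed by a false improving trend

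*Combined protocol and SAP*

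**What the plan says.** The Quantitative Analysis paragraph of Aim 3 fits each outcome by generalized estimating equations within an interrupted time series. Two results are wanted: the "change in the average level of each outcome in the post period" against the time before, "as well as changes in the trends in each outcome". On the terms that carry them, the plan says: "The key variables will be an indicator of the ACO enrollment period and its interaction with time trends". Its worked example reads a trend change as access to specialists growing faster or slower than before the ACO.

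The change point is a single date. Key treatment variable places assignment in the "34-county service area in Ohio beginning in July 2013". General Approach says: "After the policy change went into effect in July 2013, all ABD children were required to enroll in managed care". The comparison is with the same children's earlier data: "Data from PFK-enrolled children prior to enrollment (July 2010 – June 2013) will serve as primary controls".

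I found no phase-in period, excluded months, separate early term, curved post-switch trend, or sensitivity analysis on the change point. The qualitative Aim 1, by contrast, covers participants' accounts of "their experiences before, during and after the policy change".

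**The concern.** About 8,000 disabled children changed payment arrangement at once. Study Justification records that they had long been kept out of managed care over concerns about "provider network adequacy, experience, and willingness to serve this population". A temporary loss of access while families and plans adjusted is therefore plausible, although the documents do not say it happened. The plan recognises a period during the change in Aim 1 but gives it no term in Aim 3.

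With one level and one slope after the switch, a short-lived harm followed by recovery cannot be fitted as such. The best straight line starts on the adverse side and slopes towards the favourable side. A return to normal is then read as outcomes improving over time under the ACO, which is the direction of the study hypothesis. The document says families and other ACOs are to use the results to weigh advantages and disadvantages. They would want the risk around the move separated from the longer-run effect.

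**Working it through.** The plan gives no numerical figure for this model, so there is none to reproduce. The check fits the planned terms to a course whose true lasting effect is zero.

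**Inputs from the documents.** Pre-period July 2010 to June 2013, 36 months (Key treatment variable). Post-period n = 36 months if the six-year period in Sub-group analysis applies, or up to 42 (July 2013 to December 2016) from the claims years 2010–2016. Person-month file (Procedures, Aim 3, Assumptions).

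**Assumptions.** Flat pre-period; a rise of 1 unit in an adverse outcome in the first k post-switch months, then full return; linear scale; equal weight per month; time t = 0 in the first post-switch month. For outcomes where higher is better, the signs reverse and the reading is the same.

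**Formulas.** The indicator and its interaction give the post-period its own line, so least squares there gives:

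- mean shift = k/n
- slope per month = −6k(n − k) / [n(n² − 1)]
- level at the switch = k/n − slope × (n − 1)/2
- fitted value in the last month = k/n + slope × (n − 1)/2

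For n = 36, k = 6: slope = −6·6·30/(36·1295) = −1080/46620 = −0.0232 per month, or −0.28 per year. Level = 0.167 + 0.0232·17.5 = +0.57. Last month = 0.167 − 0.405 = −0.24.

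| n | k | Mean shift | Level at switch | Slope per year | Last month |
|---|---|---|---|---|---|
| 36 | 3 | 0.08 | +0.31 | −0.15 | −0.14 |
| 36 | 6 | 0.17 | +0.57 | −0.28 | −0.24 |
| 36 | 12 | 0.33 | +0.98 | −0.44 | −0.32 |
| 42 | 6 | 0.14 | +0.50 | −0.21 | −0.22 |

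After month k every true value is zero. With n = 36 and k = 6 the fitted effect crosses zero at 17.5 + 0.167/0.0232 ≈ 25 months and is falsely favourable from then on. A disruption that fades linearly over 6 months gives +0.35, −0.17 per year and −0.15.

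**Would it reach significance?** Take 12 pre- and 12 post-quarters, 8,080 children, and a disruption of two quarters. Assume event rates of 0.1 or 0.5, within-child correlation 0 to 0.6, and common quarterly shocks with SD 0 to 1 percentage point. A 5-point disruption gives p < 0.05 for the false trend with probability 0.73 to 1.00; a 2-point disruption, 0.18 to 1.00.

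**Does a window repair it?** Leaving out the first w months returns exactly zero for level and trend if w ≥ k. Two variants do less well:

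- *Window too short* (6 months left out, disruption of 12). The remaining 30 months start with 6 disrupted ones: slope = −6·6·24/(30·899) = −0.0320 per month, or −0.38 per year; level = 6/30 + 0.0320·20.5 = +0.86. Most of the bias stays.
- *One indicator for the whole window*, when the disruption is shorter. The common slope still picks up the pattern inside the window. For w = 12, k = 6: slope = −18/(143 + 1150) = −0.0139 per month, or −0.17 per year; level = 0.0139·23.5 = +0.33. For w = 6, k = 3 the remainder is small: +0.04 and −0.02 per year.

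**Precision.** With independent monthly errors of variance σ², the variance of the level change is σ² times the sum of 1/m + t̄²/S over the two periods, where m is the number of months used, t̄ their mean time and S = m(m² − 1)/12. The pre-period gives 0.1159. The post-period gives 0.1066 with all 36 months, and 0.1510, 0.2203 and 0.5219 after leaving out 3, 6 and 12. The standard-error ratios are √(0.2668/0.2225) = 1.095, √(0.3362/0.2225) = 1.23 and √(0.6378/0.2225) = 1.69.

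**Annual measures.** Three post-switch points with values 0.5, 0, 0 give a level of +0.42 and a slope of −0.25 per year. Removing the first year leaves two points, which a line fits exactly.

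**The case against.** The strongest reply is that the disruption is a supposition. A reader might infer from Study Justification that the authors expected or knew of harm at the switch. The text supports neither: it gives past reasons for exemption, and a poor network would be a lasting problem rather than a brief one. Some facts point the other way. The ACO dates from 1994, already served more than 300,000 Medicaid children, and still pays physicians per service. This stands, so the point is conditional.

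A reader might also infer that the harm would be hidden, or that a lasting effect of 0.57 would be reported. Neither follows. The plan reports level and trend together, so an adverse step would be visible and would count against the hypothesis. The 0.57 depends on centring time at the switch, which the plan does not specify; if the level result means the average post-period shift, it is 0.17. The slope does not depend on this choice.

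Nor does the plan rule out further terms: it names key variables, not a complete model. But none is planned for a transition.

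It can be said, too, that the effect of switching includes the transition. That is fair for an overall average. It does not justify reading recovery as a trend produced by the ACO.

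Finally, the plan would use qualitative findings to explain quantitative patterns and would review alternative explanations with the advisory panel. Both are unspecific, and the panel review follows preliminary results; neither changes the estimates. The possible comparison with other Ohio regions is no sure remedy either, since those children also had to enter managed care in July 2013 and may share any disruption.

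**Conclusion.** The concern holds conditionally. The planned terms cannot distinguish a temporary disruption from a worse start followed by real improvement, and nothing else in the plan does so reliably. Per unit of disruption, 3 to 6 months of it with 36 post-switch months produces a false trend of −0.15 to −0.28 units per year and an apparent benefit of 0.14 to 0.24 in the last month. The average post-period level moves only 0.08 to 0.17. The direction was the same for abrupt, linear and exponential recovery; the size depends on the assumed length and shape, and on a linear scale. This is a weakness in how a trend change may be interpreted. It is not evidence that harm occurred, nor that the analysis would conceal it.

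**What to change.** For outcomes measured monthly or quarterly, pre-specify a second analysis that leaves out the transition months or gives each transition month or quarter its own indicator, with windows of 3, 6 and 12 months from July 2013. One indicator for a whole window is not enough, for the reason shown above. Report this beside the planned model and plot the observed post-switch series. State in advance that a trend change will not be read as an ACO improvement unless it persists once the window is removed. Report the window estimates for emergency department use, hospitalisation and specialist access as results in their own right. For outcomes specified only annually, state that a transient cannot be separated from a trend.

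The person-month file already planned is sufficient, so no new data are needed. The cost is precision: under the independence assumption and with 36 post-switch months, the standard error of the level change rises by about 9.5% with a 3-month window, 23% with 6 months and 69% with 12 months. The 12-month window is therefore better used as a sensitivity analysis than as the main result. A recovery that outlasts the chosen window will still leave bias, which is why several lengths are needed.
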